#### 6.2.1 From Screening to Event Participation

There are no restrictions on use of IQOS or cigarettes or any other tobacco or nicotine-containing products during screening until participation in any of the events.

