#### Confidentiality Statement

Data and information contained in this document are considered to constitute trade secrets and confidential commercial information, and the legal protections provided to such trade secrets and confidential information are hereby claimed under the provisions of applicable law. No part of this document may be publicly disclosed without the written consent of Philip Morris Products S.A

---

---

Related to PMI\_RD\_WKI\_000759

In addition, a total of  $20\% \pm 5\%$  of the available seats at the Event location of actively exposed IQOS Users (who use IQOS during the event) will participate in each of the Exposure Events.

Participants actively using IQOS will enter the event location first and start using IQOS *ad libitum* for 1h prior to the other participants (passive Exposure Group) entering the event location.

IAQ measurements will be sampled for up to 3h prior to the start of the Event and for 3h after the last participant was exposed for 1h. Urine specimens per person will be collected for analysis as follows:

The first urine sample will be collected prior to the start of the event. For the second urine sample, collection will only start with the first void after 2 hours of IQOS exposure to allow sufficient exposure to have occurred and therefore detection of BoExp in the urine. From the 2h time point onwards every subsequent void will be collected and the previous urine sample discarded with the last void collected ideally at the end of the 4h exposure period. Only the first and the last urine sample taken (ideally after 4h of exposure) will be analyzed. The time of urine collection will be recorded to ensure that only urine samples taken after 2 hours exposure to IQOS are analyzed.

A fixed menu of food and non-alcoholic and alcoholic beverages typically served in Japanese restaurants will ensure homogeneity of types of potential confounders of both IAQ endpoints and BoExp in the unexposed and passively-exposed participant groups. The overall amount of food consumed per food type and beverages consumed by type will be recorded.

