#### 6.2.2 Non-Exposure Event

Participants will not be permitted to use IQOS, cigarettes or any other tobacco or nicotine-containing products during the 4-hour Non-Exposure Event.

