#### 6.2.3 Exposure Event

IQOS Users assigned to the Active Exposure Group will be permitted to use exclusively IQOS during the 4-hour Exposure Event. All other participants will not be allowed to use any tobacco or nicotine-containing products for the duration of their participation in the event.

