## 6.6 Restrictions

### 6.6.1 General Restrictions

As the study objective is to represent a real life setting, no restrictions apply to any of the participants other than stated in the Inclusion/Exclusion criteria (i.e., with regards to smoking prior to the events, wearing perfume, dress code, etc.)

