**Table 8 Schedule – Exposure Event**

Time	Sample collection	Procedures	Additional information
Start of procedure	Exposure Event		
IAQ Assessment	IAQ	See section 7.3.8	For 3h prior to the first participant entering the Event location
Arrival and Check-In		Participant Identification, check if ICF has been signed Confirmation of demographics data Tobacco or nicotine-containing product use self-reporting Readiness to comply to study procedures Self-Reported Health Outcomes and Events Questionnaire	Sex, date of birth, ethnicity Participant to fill questionnaire
Check assignment of IQOS Users		Check assignment of IQOS Users into the Active Exposure or Passive Exposure Group	Participants who are self-reported IQOS Users and have brought their device and HeatSticks
Prior to entering the Event	U	Spot urine collection for NEQ, total NNAL, total NNN, 3-HPMA, HMPMA, HEMA and creatinine samples.	Process samples BoExp analysis according to laboratory manual/SHM.
“Priming” of Event location		The Active Exposure Group will enter the event location approximately 1h before the Passive Exposure Group to start using IQOS.	
During the Event		Dinner and Drinks	Food typically served in Japanese restaurants, soft-drinks, tea, alcoholic

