5.2 Definition of Special Terms

The following special terms are used in this SAP:

Baseline	Baseline is defined as the observation recorded prior to entering the event room.
Duration of exposure (Actively Exposed)	The duration of exposure for actively exposed participants is defined as the time that a participant is allowed to use IQOS after entering the event room for priming until the time of last urine void.
Duration of exposure (Passively Exposed)	The duration of exposure for passively exposed participants is defined as the time that a participant enters the event room until the time of last urine void.
Product Use Status	For each participant, the product use categories were defined based on the Self-Reported Tobacco and Nicotine-Containing Product Use Questionnaire.

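### The no-use rule starts after the baseline urine, so smokers' and IQOS users' own product use before room entry would count as change after passive exposure

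*Protocol*

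**What the plan says.** **Product use.** Protocol 6.2.1 places no restriction on IQOS, cigarettes or "any other tobacco or nicotine-containing products during screening until participation in any of the events". Section 6.6.1 repeats this for real-life reasons: "no restrictions apply to any of the participants other than stated in the Inclusion/Exclusion criteria (i.e., with regards to smoking prior to the events". The ban is tied to the event itself. For Non-Exposure Events, 6.2.2 says "Participants will not be permitted to use IQOS, cigarettes or any other tobacco or nicotine-containing products during the 4-hour Non-Exposure Event". For Exposure Events, 6.2.3 says of everyone outside the Active Exposure Group: "All other participants will not be allowed to use any tobacco or nicotine-containing products for the duration of their participation in the event". Section 6.6.3 has the same span.

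**Baseline.** Protocol 4.1.3 states "The first urine sample will be collected prior to the start of the event", and 4.1.2 says the same for Non-Exposure Events. Tables 7 and 8 put this sample after check-in and before entry. SAP 5.2 agrees: "Baseline is defined as the observation recorded prior to entering the event room".

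**Outcome.** SAP 12.6.1.1 models the change from that baseline to the last void and estimates it for each product use group. The primary objective (Protocol 3.1, SAP 6.1) asks for results by product use status.

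**Duration of exposure.** Protocol 12.4 counts from the pre-event urine collection. SAP 5.2 counts from room entry for passively exposed participants.

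**The concern.** The window over which change is measured opens at the baseline void. The window in which own use is forbidden opens later, with the event or participation in it. A Cigarette Smoker or IQOS Passive User who gives the baseline sample and then uses a product before entering breaks no written rule on the natural reading. That intake comes after baseline, so adjusting for baseline does not remove it. It reaches the last void and is reported as part of the change after passive exposure.

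Protocol 2.2 includes the two user groups to see whether IQOS adds measurable exposure in people who already carry some from their own use. NEQ, a co-primary endpoint, includes free nicotine, so own use feeds directly into it. An unrecorded own unit cannot be separated from a passive effect in these groups.

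**Working it through.** **1. Order of steps for a passive participant**

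| Step | Source | Own use banned? | Inside the change window? |
|---|---|---|---|
| Before check-in | Protocol 6.2.1, 6.6.1 | No | No |
| Baseline void | Protocol Tables 7–8; SAP 5.2 | No | Window opens |
| Void to room entry | No rule, time limit or record of use | Not as written | Yes |
| Room entry to last void | Protocol 6.2.2, 6.2.3, 6.6.3 | Yes | Yes |

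The third row is the gap.

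**2. Would any safeguard catch it?**
- Protocol 6.5.2: staff at the location check for use during the events.
- Protocol Tables 7 and 8: the closing confirmation concerns products that the protocol does not allow. Use in the gap is not expressly disallowed.
- Protocol 6.2: urine is used to check smoking status and compliance during the events. The only cut-off given (SAP 7.1.2, total NNAL above 75.9 pg/mL) applies to Non-Smokers.
- SAP Table 3: the check-in questionnaire covers the past 12 months and past 30 days, not time of last use.
- SAP duration covariate: it starts at room entry, so the model carries no information on the gap.

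**3. Number who could be affected**

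The minimum is 169 per event type (Protocol 12.2), with 25% in each user group (Table 1).
- Each user group: 0.25 × 169 = 42.25, about 42.
- Both together: 0.50 × 169 = 84.5, about 84.
- Reading ±5% as percentage points, each group runs from 0.20 × 169 = 33.8 to 0.30 × 169 = 50.7.

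These are people to whom the gap applies, not people known to have used it.

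**4. Illustration of bias (inputs assumed)**

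The documents give neither the share f of a user group that uses a product in the gap nor the fold rise r in the biomarker from that use. Results are geometric means, so the last-void-to-baseline ratio is multiplied by exp(f × ln r).

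| f | r = 1.1 | r = 1.25 | r = 1.5 | r = 2 |
|---|---|---|---|---|
| 0.10 | 1.010 | 1.023 | 1.041 | 1.072 |
| 0.25 | 1.024 | 1.057 | 1.107 | 1.189 |
| 0.50 | 1.049 | 1.118 | 1.225 | 1.414 |

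Example: f = 0.25, r = 2 gives exp(0.25 × 0.693) = 1.189.

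**5. Between-event contrast**

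SAP 14.1 says that the planned model did not compare event types and adds the Exposure to Non-Exposure ratio post hoc. The bias factor there is exp((f at Exposure − f at Non-Exposure) × ln r).
- Equal shares: 1.000.
- 0.50 against 0.25: 1.024 (r = 1.1) to 1.189 (r = 2).
- 0.25 against 0.50: 0.976 (r = 1.1) to 0.841 (r = 2).

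The contrast removes the error only when gap use is the same at both event types. Otherwise it can err in either direction.

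**The case against.** **Participation may begin at check-in.** The term is not defined. Tables 7 and 8 list check-in and baseline urine as steps of the event schedule, and Appendix A puts registration under the events. On that reading the ban already covers the gap. This is possible, but it fits poorly with 6.2.2, which ties the ban to the 4-hour event, with the 2-hour count from entry in Table 7, and with SAP 5.2. If it is what the sponsor meant, one sentence settles it.

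**The main result is untouched.** This stands. Protocol 2.2 aims at Non-Smokers, and SAP 12.6.1.1 names them for the main contrast while leaving those for other groups optional. Stratified results are nevertheless part of the primary objective. Gap use at Exposure Events would also raise the users' apparent change, which works against the finding of no increase that the study hopes for.

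**Use just before the void matters too.** This also stands. Protocol 4.1.3 waits 2 hours for biomarkers to appear in urine, so a unit used minutes before baseline may show mainly in the last void. Moving the start of the rule does not remove that source; a question on last use addresses it.

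**A longer gap at Exposure Events.** Table 8 says "The Active Exposure Group will enter the event location approximately 1h before the Passive Exposure Group to start using IQOS", and a reader might infer that passive participants void first and then wait through priming. The documents do not say when they check in or void relative to priming, and separate arrival is equally compatible with the text. A longer gap at Exposure Events is therefore not established.

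**Conclusion.** The point holds as a gap in the written rules, and closing it is a worthwhile, inexpensive improvement. The baseline void precedes the start of the no-use rule, and no provision covers own use in between. About 84 of 169 participants per event type belong to the groups concerned.

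The size of the bias is unknown. The factors in the working, from 1.010 to 1.414, rest wholly on assumed shares and fold rises. A reader might instead express one unit as a fraction of a day's consumption, but that describes intake and not the biomarker, and the documents give no usual daily consumption.

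Two other inferences would go too far. The documents show that such use is not excluded, not that it happened. They also give no ground to doubt the Non-Smoker result on this account, provided those participants are truly abstinent. The conclusion assumes that participation starts at room entry or event start, which is the more natural reading but not a stated definition.

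**What to change.** 1. In Protocol 6.2.1–6.2.3, 6.6.3 and Tables 7–8, state that for Non-Exposed and Passive Exposure participants the no-use rule starts when the baseline urine is collected.
2. Add a check-in item on time and type of last product used. Use it as a covariate or in a sensitivity analysis for Cigarette Smokers and IQOS Passive Users. This also addresses use shortly before baseline.
3. Tabulate baseline-void-to-entry time by event type and user group. Protocol 12.4 already needs the first time and SAP 5.2 the second, so little or no new data should be required.
4. Reconcile the two definitions of exposure duration (Protocol 12.4, SAP 5.2).

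The cost is one extra question, a wording change and slightly longer abstinence for users. Staff need to make the earlier start known at check-in. SAP version 3.0 was written after results had been reviewed, so items 1 and 2 can help only further events or a repeat study. For data already collected, item 3 and a stated limitation on the user-group results are what remain.

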#### 6.2.2 Non-Exposure Event

Participants will not be permitted to use IQOS, cigarettes or any other tobacco or nicotine-containing products during the 4-hour Non-Exposure Event.

#### 6.2.3 Exposure Event

IQOS Users assigned to the Active Exposure Group will be permitted to use exclusively IQOS during the 4-hour Exposure Event. All other participants will not be allowed to use any tobacco or nicotine-containing products for the duration of their participation in the event.

#### 6.2.4 In-between Event Participation

There are no restrictions on use of IQOS, cigarettes, or any other tobacco or nicotine-containing products, during the periods between participation in Events.

### 6.3 Method for Assigning Subjects to Study Groups

In the Non-Exposure Events, participants will be assigned to the IQOS User Group, Cigarette Smoker Group, or Non-Smoker Group based on self-reported smoking status.

The same applies to the Exposure Events with the exception that IQOS Users will be assigned during the enrollment process to be either an IQOS User who is allowed to use IQOS during the Event (Active Exposure Group), or an IQOS User who is not allowed to use any tobacco or nicotine-containing products for the duration of their participation in the event. The assignment to either of the two groups will be automatically done by the system with the Active Exposure Group to be filled first to ensure that the necessary sample size for the Active Exposure Group can be assured for each of the events.

### 6.4 Blinding

There is no blinding in this study.

---

## 6.5 Investigational Product Accountability and Compliance

### 6.5.1 Dispensing Investigational Product

Participants in the Active Exposure Group will be asked to bring their own *HeatSticks* for their own use during the entire study period as *HeatSticks* will not be provided by the Sponsor. Participants in the Active Exposure Group will use IQOS *ad libitum* with no flavor restrictions.

### 6.5.2 Adherence to allocated Exposure

Adherence to allocated Exposure, no use of any tobacco or nicotine-containing product during the Non-Exposure Events and no use of any tobacco or nicotine-containing product during the Exposure Events, with the exception of the Active Exposure Group, will be monitored by the staff at the Event location. Any product use by any participant in the Passive Exposure Group and any product use other than IQOS in the Active Exposure Group will lead to the discontinuation of the participant from the study.

## 6.6 Restrictions

### 6.6.1 General Restrictions

As the study objective is to represent a real life setting, no restrictions apply to any of the participants other than stated in the Inclusion/Exclusion criteria (i.e., with regards to smoking prior to the events, wearing perfume, dress code, etc.)

### 6.6.2 Dietary Restrictions

For the duration of an Event, participants will only be allowed to consume food and drinks provided at the Event location. Participants will not be allowed to bring in their own food or beverages. The food and beverages served during the event represent a typical and often requested choice in Japanese restaurants, however it can only represent a sub-selection of choices available in the variety of restaurant settings.

### 6.6.3 Product Use Restrictions

Participants in the Active Exposure Group will only be allowed to use IQOS. IQOS use in the Active Exposure Group is not limited in terms of *HeatStick* variants or number of *HeatSticks* used. All other participants will not be allowed to use any tobacco or nicotine containing product for the duration of the event. Any product use other than allocated will be recorded by the study staff and checked by the Principal Investigator or designee.

---

## 7 STUDY PROCEDURES

An overview of all study procedures is shown in the schedule of events (see Appendix A). In this section, only the expected/planned time points for the various measurements are described.

### 7.1 Informed Consent

Prior to participating in any Event, the participant will be asked to provide their consent to participate to the study (ICF) ([section 1.3.1](#)).

### 7.2 Debriefing on IQOS

A debriefing of participants will be done at each Event to address any intended or unintended beliefs participants may have about IQOS, and to inform participants on the current status of knowledge about IQOS. The goal of the debriefing is to ensure that participants have an accurate understanding of product risks including an understanding that IQOS has not been demonstrated to be less harmful than cigarettes.

### 7.3 Main Assessments

#### 7.3.1 Questionnaires

The participant questionnaires used in this study will be entered by the participant directly in the CASI survey. All questionnaires, as well as instructions will be provided in Japanese (the local language).

See [Appendix A](#) for the time points of assessment.

#### 7.3.2 Demographics

Demographic data corresponding to inclusion/exclusion criteria (i.e., sex, age, and ethnicity) will be recorded in the screening domain.

See [Appendix A](#) for the time points of assessment.

#### 7.3.3 Self-reported tobacco and nicotine-containing product use

The self-reported tobacco and nicotine-containing product use questionnaire will be administered at enrollment within the CASI and during the check-in procedures of each event to confirm self-reported product use status.

See [Appendix A](#) for the time points of assessment.

---

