8.3.1 Self-reported tobacco and nicotine-containing product use

The self-reported tobacco and nicotine-containing product use questionnaire will be administered at enrollment within the CASI and during the check-in procedures of each event to confirm self-reported product use status.

The questions on Smoking History/Habits are self-administrated, to be answered by participants. No imputation for missing data will be performed.

The questions on product use are shown in Table 3.

Table 3. Self-Reported Tobacco and Nicotine Containing Tobacco Product Use

Question	Answer
1.1* Have you smoked at least 100 cigarettes in your ENTIRE LIFE?	Yes / No
1.2 In the past 12 months, did you smoke cigarettes?	Yes / No
1.3 In the past 30 days, did you smoke cigarettes...	Every day/Some days/Not at all
1.4 On how many of the past 30 days did you smoke cigarettes?	Numeric response, 2 digits
1.5 On average, on those days you smoked, how many cigarettes did you usually smoke each day?	Numeric response, 3 digits
2.1* Have you used at least 100 IQOS HeatSticks in your ENTIRE LIFE?	Yes / No

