**Table 3. Self-Reported Tobacco and Nicotine Containing Tobacco Product Use**

	Question	Answer
2.2	In the past 12 months, did you use IQOS with HeatSticks ?	Yes / No
2.3	In the past 30 days, did you use IQOS with HeatSticks ?	Every day/Some days/Not at all
2.4	On how many of the past 30 days did you use IQOS with HeatSticks ?	Numeric response, 2 digits
2.5	On average, on those days you smoked, how many cigarettes did you use IQOS with HeatSticks ?	Numeric response, 3 digits
2.6	In the past 12 months, did you use a Heat-not-burn product other than IQOS with HeatSticks ?	Yes / No
2.7	In the past 30 days, did you use a Heat-not-burn product other than IQOS with HeatSticks ?	Every day/Some days/Not at all
2.8	On how many of the past 30 days did you use a Heat-not-burn product other than IQOS with HeatSticks ?	Numeric response, 2 digits
2.9	On average, on those days you smoked, how many cigarettes did you use a Heat-not-burn product other than IQOS with HeatSticks ?	Numeric response, 3 digits
3.1	In the past 12 months, did you use an e-cigarette?	Yes / No
3.2	In the past 30 days, did you use an e-cigarette?	Every day/Some days/Not at all
3.3	On how many of the past 30 days did you use an e-cigarette?	Numeric response, 2 digits
3.4	On average, on days you used, how many times did you usually use an e-cigarette each day?	Numeric response, 3 digits

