12.6 Planned Statistical Analyses

12.6.1 Primary Analysis

12.6.1.1 Statistical Analysis of Primary Endpoints

For each urinary BoExp in the primary analysis NEQ, Total NNAL, Total NNN, the change between pre-event and end of study levels adjusted for creatinine will be modeled using a linear model in the Compliant Exposure Set.

The SAS procedure PROC MIXED will be used with the restricted maximum likelihood method for estimation of the parameters. The mixed model will have the change from baseline as dependent variable and the following covariates will be included in the model: Baseline, Sex, Event Type (Exposure or Non-Exposure), Duration of Exposure, Product Use Status, Product Use Status by Event Type interaction for all BoExp. In addition, an air quality covariate related to each BoExp is included in the model depending on the endpoint and is described in Appendix 15.2. This table also specifies the various IAQ covariates that are assessed using a step-wise regression approach for each BoExp. The algorithm is described below,

1. Fit a full model with all covariates

2. Drop one IAQ covariate and re-fit the model.
3. Perform a likelihood ratio test and drop the IAQ covariate with the largest p-value for the likelihood ratio statistic if it is more than 0.05.
4. Repeat steps 2 and 3 until no more IAQ covariates can be dropped.
5. Refit the final model with the IAQ covariates remaining in the model and estimate exposures for each product use group.

Appropriate contrasts will be constructed to determine the effect of passive exposure to IQOS aerosol during the Exposure Event on the mean change in levels of urinary BoExp together with the 95% CIs for non-smokers during an Exposure Event. Other contrasts can be constructed to determine the change in urinary BoExp for participants with other smoking status (Cigarette Smoker and IQOS Passive Users) after passive exposure to IQOS usage.

An example of SAS code for the final model is provided below,

```
Proc mixed data=_data_ method=reml;
Class event_type sex product_use;
Model endpoint = baseline sex event_type product_use event_type*product_use
duration <IAQ covariates> / ddfm=kr;
estimate 'Cigarette Smoker' intercept 1 baseline xx sex .5 .5 product_use 1 0 0
event type 1 event_type*product_use 1 0 0 0 0 duration xx IAQ1 xx ... IAQn xx /
alpha=0.05 cl;
Run;
```

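### Time of last product use before the baseline void is not recorded, so in Cigarette Smokers and IQOS Passive Users own-product washout is mixed with passive exposure, and its balance between event types cannot be checked

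*Protocol*

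**What the plan says.** Protocol 7.3.3 says that the product-use questionnaire is "administered at enrollment within the CASI and during the check-in procedures of each event to confirm self-reported product use status". SAP 8.3.1, Table 3, prints its items. The cigarette block runs from a lifetime item through "In the past 30 days, did you smoke cigarettes" to "On average, on those days you smoked, how many cigarettes did you usually smoke each day". The IQOS block has the same structure; one of its items begins "On how many of the past 30 days did you use IQOS with". The two lifetime items are asked only at enrolment. No item asks for the date or time of last use, and no check-in step in Protocol Tables 7 and 8 or Appendix A records it.

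Use before arrival is left open. Protocol 6.2.1 sets "no restrictions on use of IQOS or cigarettes or any other tobacco or nicotine-containing products during screening until participation in any of the events". Protocol 6.6.1 adds that "no restrictions apply to any of the participants other than stated in the Inclusion/Exclusion criteria (i.e., with regards to smoking prior to the events".

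SAP 5.2 takes the void before room entry as baseline and counts duration of exposure from room entry to the last void. The model in SAP 12.6.1.1 contains "Baseline, Sex, Event Type (Exposure or Non-Exposure), Duration of Exposure, Product Use Status", the interaction of product use with event type, and air quality terms. SAP Table 8 repeats this list for all seven biomarkers, and SAP 12.6.2.2 analyses the secondary markers in a similar way.

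Protocol 2.2 and SAP 3 explain why the two user groups are there: to see whether IQOS adds measurably to the exposure that these people already have. SAP 14.1 acknowledges that the planned model gave estimates per group and event type without comparing event types, and adds that comparison post hoc.

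**The concern.** A smoker who uses a product minutes before the baseline void is still absorbing and converting that dose during the event. One who stopped hours before is already clearing it. Their biomarker changes over the next 4 h differ for reasons unrelated to the air in the room. The time that would distinguish them lies before both the baseline void and the duration clock, so neither dates it.

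Two things are at stake. First, the planned estimate for users in the Exposure Event is a change within one event type, so the kinetics of their own product are part of it. Second, the between-event comparison is free of this only if recency of use is alike in the two event types, and without a record nobody can show that it is. Abstaining users make up half of each non-using group (25% plus 25%), and the primary objective is stratified by product use status.

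**Working it through.** **Inputs.** From the documents: 169 participants per event type, with 25% Cigarette Smokers and 25% IQOS Passive Users (Protocol Table 1), so 0.25 × 169 = 42.25, about 42 per user group per event type; about 4 h per participant; covariates as in SAP 12.6.1.1. The documents give no half-lives, variances or use patterns, so all kinetics below are assumptions. The figure of 169 cannot be reproduced, since no effect size, SD, alpha or power is stated. The point does not depend on it.

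**Step 1: own-product decline with no passive exposure.** First-order change over 4 h = 100 × (2^(−4/h) − 1) for half-life h.

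| Half-life | 2 h | 4 h | 8 h | 16 h | 24 h |
|---|---|---|---|---|---|
| Change | −75% | −50% | −29% | −16% | −11% |

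**Step 2: dependence on last use.** Take hourly use, first-order appearance (half-time 0.5 h) and elimination, and voids covering −2 to 0 h and 2 to 4 h. With last use 0.1, 1, 2 and 4 h before the baseline void, the log change is −0.61, −0.91, −1.18 and −1.36 for a 2 h half-life, and −0.04, −0.10, −0.15 and −0.17 for 16 h. Across appearance half-times of 0.5 to 1 h and different assumed histories of earlier use, the shift from 0.1 h to 4 h is about 0.75 to 0.78 (2 h half-life), 0.24 to 0.33 (6 h) or 0.09 to 0.22 (16 h). These are raw changes, without baseline adjustment.

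**Step 3: after baseline adjustment.** The simulated level at time T after last use is D·kp/(kp − km)·(e^(−km·T) − e^(−kp·T)) + B·e^(−km·T), with k = ln 2 / half-life. Parent half-life is 2 h, and metabolite half-life 4, 8 or 16 h. D and B are log-normal (log means 0 and 1, log SD 0.7), T is exponential, time to last void is uniform on 2.5 to 4.5 h, and noise SD is 0.2 per log level. There are 42 users per event type, 400 replicates and **no passive effect**. Log change was regressed on event type, baseline and duration; sex and air quality terms were left out. Ratios are given for metabolite half-lives 4 / 8 / 16 h.

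| Mean T, Exposure vs Non-Exposure | Change in Exposure Event alone | Exposure / Non-Exposure | CIs excluding 1 |
|---|---|---|---|
| 1 h vs 1 h | 0.72 / 0.94 / 1.07 | 0.998 / 0.999 / 0.995 | 5.5% / 5.5% / 6.5% |
| 0.5 h vs 1 h | 0.75 / 0.98 / 1.11 | 1.04 / 1.04 / 1.03 | 7.5% / 7.7% / 5.0% |
| 0.5 h vs 2 h | 0.75 / 0.98 / 1.12 | 1.11 / 1.10 / 1.07 | 34% / 24% / 17% |
| 2 h vs 0.5 h | 0.69 / 0.89 / 1.02 | 0.89 / 0.91 / 0.93 | 35% / 31% / 18% |

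The single-event change departs from 1 in either direction although nothing was inhaled passively. The between-event ratio is clean when recency is equal, and off by 3% to 11% when mean last-use time differs by 0.5 to 1.5 h. The Monte Carlo standard error of a 5% rate is √(0.05 × 0.95/400) = 1.1 points, so the excess in the 0.5 h row is slight at most.

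**Step 4: precision.** Under the pulse kinetics of Step 2, last-use time explains about 17 to 39% (2 h half-life), 3 to 10% (6 h) or 1 to 5% (16 h) of the baseline-adjusted variance in users. The residual SD shrinks by 1 − √(1 − R²): 9 to 22%, 2 to 5%, and 0.5 to 2.5%.

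**The case against.** The strongest reply is that the design already has its control. Non-Exposure Events enrol the same user groups in the same proportions, under the same abstinence rule, restaurant and void schedule, and SAP 14.1 compares the two event types within each group. With equal recency that contrast shows essentially no bias (first row of the table). This stands. What remains is that the contrast is post hoc, and that equality is assumed: participants pick their dates (Protocol 4.1.1), allocation to event type is not randomised, and recency is not recorded.

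A reader might infer that the plan treats the users' change as a proven effect of IQOS. It does not go that far. SAP 12.6.1.1 reserves the effect contrast for Non-Smokers and speaks only of change for the other groups, although Protocol 2.2 and SAP 3 show that this change is meant to bear on additive exposure. Non-Smokers are the main target and have no last-use time, so their estimates are not biased.

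It is also tempting to call recency wholly unadjusted and the main driver of the change. Baseline level is a covariate and may partly reflect recency. It need not carry much of it: in a simulation with use intensity at log SD 0.7, mean last use 1 h before and noise SD 0.2 per void, baseline correlated only −0.16 to 0.02 with last-use time. As the documents give no kinetics, how large a driver recency is remains unknown.

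Finally, a 1 h difference can be made to look like a 26% bias: −0.91 − (−0.61) = −0.30, and e^(−0.30) = 0.74. That puts everyone at 0.1 h against everyone at 1 h, uses a 2 h half-life tied to no endpoint, and ignores baseline adjustment. It is not a fair size for this model.

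**Conclusion.** The point holds for the two user groups. Time of last use is not recorded, and the models reach it only through the baseline level. The users' single-event change in SAP 12.6.1.1 and 12.6.2.2 therefore cannot separate their own product from passive exposure. The contrast in SAP 14.1 removes what is common to both event types. Any remaining bias needs an imbalance in recency, which the documents neither show nor allow anyone to rule out. If mean last use differed by 0.5 to 1.5 h, the bias would be roughly 3 to 11% with baseline held equal, under the kinetics assumed in Step 3.

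The precision gain for users is material for fast-clearing markers and small for slow ones. Non-Smoker confidence intervals are touched only through the pooled residual variance. Assuming another residual SD of 0.3 to 0.5 and mean last use of 0.5 to 2 h, pooled CI width grows by under 0.5% (16 h half-life), under 3% (6 h) or about 2 to 21% (2 h). The change is worth making, but nothing here overturns the Non-Smoker result.

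**What to change.** 1. In Protocol Tables 7 and 8, add one check-in item for users: product and clock time of last use.
2. In SAP 12.6.1.1, 12.6.2.2 and 14.1, add time from last use to the baseline void (log or capped) as a covariate for Cigarette Smokers and IQOS Passive Users, set to zero for Non-Smokers through an interaction with product use.
3. Evaluate both event types at a common value of this covariate. This needs stating, because SAP 14.1 enters each covariate at its difference between event types, which would put a recency imbalance back into the estimate.
4. Base the users' conclusion on the Exposure versus Non-Exposure contrast.

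The cost is one question, one covariate and a few degrees of freedom. Self-reported times carry recall error, and time alone does not capture the amount used that day.

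SAP 14 describes analyses prompted by results already seen, so the item can probably no longer be collected for this study. In that case, state the limitation in the report and do not read the users' single-event change as passive exposure.
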